8.1.3 Changes to Case Report Form (CRF) Data

Monitors will perform source data verification (SDV) as defined for the study and described in the study Monitoring Plan.

If any errors or discrepancies in the eCRFs are found during data entry or review, discrepancies will be generated programmatically within the EDC system, and 'manual' queries will be generated by either a monitor or Data Management.

Discrepancies and queries can only be corrected by the Investigator(s) or other authorised site personnel. An audit trail documents all changes to the data over the entire study period. If the reason for a change is not obvious, a comment must be supplied in the query's response, stating the reason for the change, prior to closing. The study monitor should provide guidance to Investigator(s) and the Investigator(s)' designated representatives on making such corrections.

Once queries have been resolved by the site staff, the resolutions are assessed by Data Management. If the query response provided confirms the data as correct, the discrepancy will be closed. If the response does not adequately address the question raised, a new query will be issued for further clarification.

Manual checks are performed and programs are run throughout the study until the data is clean and the database is ready for lock. All discrepancies will be resolved prior to database lock. There will be a final run of the programmed checks to ensure all discrepancies are closed out, SDV will be confirmed as complete by the monitor, and all eCRFs will be approved by the Investigator prior to database lock.

8.2 Information to Investigators

An Investigator's Brochure (IB) will be handed out to the Investigator before the start of the study. This Brochure contains all information in the Sponsor's possession necessary for the Investigator to be fully and accurately informed about the safety of *Octaplex* under evaluation and the respective benefit-risk ratio.

An updated IB will be provided by the Sponsor at regular intervals and if important new safety-relevant information concerning *Octaplex* becomes available.

The Investigators will be informed about the methods for rating relevant study outcomes and for completing CRFs.

The Investigator will be kept informed of important data that relate to the safe use of the IMP as the study proceeds.

For FP, which is the standard-of-care blood product, the corresponding label per local regulations will apply.

8.4 Investigator's Site File

At each study site, the Investigator is responsible for maintaining all records to enable the conduct of the study to be fully documented. Essential documents as required by GCP guidelines and regulations (e.g., copies of the protocol, study approval letters, all original informed consent forms, site copies of all CRFs, drug dispensing and accountability logs, correspondence pertaining to the study, etc.) should be filed accurately and kept by the Investigator for the maximum period of time required by local regulations.

The Investigator is responsible for maintaining a confidential patient identification code list, which provides the unique link between named source records and CRF data. The Investigator must arrange for the retention of this confidential list for the maximum period of time required by local regulations.

No study document should be destroyed without prior written agreement between the Investigator and the Sponsor. Should the Investigator elect to assign the study documents to another party, or move them to another location, the Sponsor must be notified in writing.

8.5 Provision of Additional Information

If errors in data transcription are encountered, a query should be raised which needs to be answered by appropriately delegated site staff. Provision of additional patient data should be avoided (except if needed for SAE reporting). In case of particular issues or governmental queries, it is also necessary to have access to the complete study records, provided that the patient's confidentiality is protected in accordance with applicable regulations.

8.6 Independent Data and Safety Monitoring Committee

An IDSMC will be established by the Sponsor. The IDSMC will be composed of recognised experts in the field of statistics, perioperative medicine and haematology who are not actively recruiting patients.

The IDSMC will review accumulating safety, endpoint and other study data (recruitment, retention and compliance, data quality and timeliness, risk versus benefit, summary statistics of outcomes) every time 100 patients have completed the study.

The IDSMC will provide recommendations about continuing, modifying and/or stopping the study based on considerations of treatment efficacy, patient safety and trial futility as appropriate. In addition, the IDSMC may make observations or recommendations to the sponsor about, but not limited to, the following:

- Efficacy of the study intervention;
- Definitions of and responses to AEs and patterns in AEs;
- Benefit/risk ratio of procedures and participant burden;
- Selection, recruitment and retention of participants;
- Adherence to protocol requirements;
- Completeness, quality and analysis of measurements;
- Amendments to the study protocol and consent forms;
- Performance of individual centres and core labs; and
- Patient safety.

A written study-specific charter will define in detail the composition, responsibilities and procedures of the IDSMC.

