Patients categorised as having an 'ineffective' haemostatic treatment response to IMP, due to requiring administration of any haemostatic intervention, including a second dose of IMP, in the time window from 60 minutes to 24 hours after initiation of the first IMP dose, will be considered as treatment failures.

Of the more than 100 patients studied in the FARES pilot study, approximately 75% of patients in the PCC group and 65% in the FP group demonstrated haemostatic treatment response from 60 minutes to 24 hours after initiation of the first IMP dose. Using a more conservative estimate of 70% versus 65%, it is estimated that 410 patients will be required to demonstrate non-inferiority with a one-sided α of 0.025, power of $\geq 90\%$, and non-inferiority margin of 0.10 when using a Farrington-Manning score test.

It is anticipated that up to 20% of randomised patients may not meet administration criteria (based on objective Bleeding Severity Scale and INR) due to cessation of haemorrhage between randomisation and delivery of IMP to the operating room and therefore will not receive the therapy.

Name of Sponsor/Company: Octapharma AG	
Name of Investigational Product: Octaplex	Protocol Identification Code: LEX-211
Name of Active Ingredient: Prothrombin complex concentrate, human	Date of Final Protocol: 25-Aug-2023

An administrative unblinded interim analysis will be carried out after approximately 200 patients have been randomised and treated and will be used to re-estimate the sample size or stop for futility (non-binding). Patient recruitment will continue during the conduct of the interim analysis. The study can only be stopped for futility and not for efficacy at the time of the interim analysis. The sample size re-estimation will be based on the evaluation of the conditional power making use of the observed response rates and inverse normal combination test statistic with equal weights given by $(\Phi^{-1}(1 - p_1) + \Phi^{-1}(1 - p_2))/\sqrt{2}$, where p_1 and p_2 denote the p-values for testing the non-inferiority null hypothesis for the first and the second stage of the trial, respectively. The aspired conditional power used for the new intended sample size will be 90%. The sample size in the second stage is limited to 210–800 evaluable patients. Accounting for dropouts as described above, the total sample size will range between 513–1250 if the study is not stopped for futility at the interim.

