3.3.1.5 Recruitment and Informed Consent

This is a pragmatic trial that compares two coagulation factor replacement therapies that are currently routinely used for the study indication in multiple regions globally and in various settings. It is not expected that participating in the trial will pose any risks to patients.

All patients ≥ 18 years old undergoing cardiac surgery with CPB at the study centres will be offered the chance to participate in the study prior to their surgery. Voluntarily given, written, informed consent will be obtained from the patient before the study procedures start. Once consent has been obtained and the patient enrolled into the study, eligibility according to inclusion criteria 1 and 4 (i.e., patients ≥ 18 years old, undergoing any index cardiac surgery employing CPB, who have provided informed consent) and the exclusion criteria will be confirmed. If screening is performed before the day of surgery, exclusion criterion 3 (i.e., severe right heart failure [clinical diagnosis \pm echocardiography]) will be rechecked on the day of surgery².

Only patients who require coagulation factor replacement therapy during surgery will be randomised, receive study drug, and undergo the proceeding visits and assessments. When the first order for PCC or FP is received by the blood bank/pharmacy while the patient is in the operating room, the blood bank/pharmacy technologist will confirm patient eligibility with the clinical team. Following confirmation of eligibility, the technologist will randomise the patient to PCC or FP according to the randomisation and dosing schedule.

²In Canada, informed consent will be obtained after randomisation, in accordance with Article 3.7A of the 2018 Tri-Council Policy Statement on the Ethical Conduct for Research Involving Humans.

Randomisation (1:1) will continue until at least 410 evaluable patients are obtained (205 patients per group).

3.3.1.6 *Blinding*

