4 STUDY POPULATION

4.1 Population Base

The study will include approximately 500 randomised bleeding adult (≥ 18 years old) cardiac surgical patients who require coagulation factor replacement after CPB. The study will continue until there are at least 410 evaluable patients, accounting for dropouts in both arms, with a minimum of 205 patients assigned to each of the two treatment groups.

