6.2.2 Planned Duration for the Study as a Whole

The study will be considered completed when at least 410 patients are consented, randomised, treated, and have finalised day 30 data. It is estimated that the study will take approximately two years for recruitment. The estimated start of the study (enrolment of first patient) is quarter 4 2022, and the estimated end of the study (last visit of last patient) is quarter 4 2024.

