9.4 Interim Analysis

An administrative unblinded interim analysis will be carried out by an independent statistician when approximately 200 patients have been randomised and treated. Unblinded information will be communicated only to the IDSMC. Possible outcomes of this analysis and recommendations to the sponsor are:

- The study will be stopped for futility. The decision to stop for futility is non-binding.
- The sample size will be re-estimated by the independent statistician.

Patient recruitment will continue during the conduct of the interim analysis. The study cannot be stopped for efficacy at the interim analysis.

The sample size re-estimation will be based on the evaluation of the conditional power, calculated as described in section 7.3 of [94] making use of the observed response rates at the time of the interim analysis and inverse normal combination test statistic with equal weights given by

$$(\Phi^{-1}(1 - p_1) + \Phi^{-1}(1 - p_2))/\sqrt{2},$$

where p_1 and p_2 denote the p-values for testing the non-inferiority null hypothesis for the first and the second stage of the trial, respectively. The aspired conditional power used for the new intended sample size will be 90%.

A 20% drop-out rate will be added to the re-estimated sample size of evaluable patients to receive the number of patients to be enrolled in the second stage.

The minimum number of patients for the second stage is 210 evaluable subjects (even if the re-estimated sample size is below this number) or 263 including the possible dropouts (+20%). The sample size for the second stage cannot exceed 1250 patients (dropouts included). If the drop-out adjusted re-estimated sample size exceeds this threshold, the IDSMC may recommend to either stop the trial for futility or to enrol the maximum number of 1250 patients.

In addition, the IDSMC will review selected unblinded summary statistics every time 100 patients have completed the study (**Section 8.6**).

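### Does naming treatment efficacy as a basis for IDSMC recommendations open an uncontrolled route to early stopping for success?

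*Protocol*

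**What the plan says.** Protocol 8.6 has the IDSMC review accumulating safety and endpoint data after every 100 completed patients and issue "recommendations about continuing, modifying and/or stopping the study based on considerations of treatment efficacy, patient safety and trial futility as appropriate". It also lists efficacy of the intervention among the topics on which the committee may advise the sponsor, and leaves its detailed procedures to a charter. Protocol 9.4 adds that, besides the interim analysis, "the IDSMC will review selected unblinded summary statistics every time 100 patients have completed the study".

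The limits on efficacy stopping stand elsewhere. The Protocol synopsis states: "The study can only be stopped for futility and not for efficacy at the time of the interim analysis". Protocol 9.4 repeats it: "The study cannot be stopped for efficacy at the interim analysis". SAP 7.4 has the same bar and does not mention the 100-patient reviews.

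On trial length, Protocol 9.4 says "The minimum number of patients for the second stage is 210 evaluable subjects", even if the re-estimated number is smaller. Protocol 3.3.1.5 says "Randomisation (1:1) will continue until at least 410 evaluable patients are obtained", and sections 4.1 and 6.2.2 set the same figure of 410.

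On testing, Protocol 9.2 and SAP 10.2 calculate one equally weighted inverse normal statistic at the end of the trial, from the stage 1 and stage 2 p-values, and compare it with 1.96. Superiority is examined only after non-inferiority has been shown.

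**The concern.** Section 8.6 lists efficacy separately from futility, so a reader may take it to mean favourable efficacy. The reviews are unblinded, cover endpoint data and recur every 100 patients. The explicit bar covers only the interim analysis. Protocol 6.2.3 also lets the sponsor, in consultation with the IDSMC, end the study at any time, so a recommendation has a path to action.

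If a review ever led to a stop with a claim of success, the plan would have no boundary, no alpha reserved for that look, and no adjusted test or confidence interval. The full one-sided 2.5% is kept for the final test. Non-inferiority and superiority are tested in hierarchy at that level, so both claims would be exposed.

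**Working it through.** **1. The plan's own figures.** Inputs from Protocol 9.1: response 70% (PCC) and 65% (FP), margin 0.10, one-sided alpha 0.025, power 90%, 1:1 allocation. For the Farrington-Manning test,

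n per arm = (z₀.₉₇₅·s₀ + z₀.₉₀·s₁)² / (0.70 − 0.65 + 0.10)².

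- The restricted null rates are 0.6192 and 0.7192, so s₀² = 0.6192 × 0.3808 + 0.7192 × 0.2808 = 0.4377 and s₀ = 0.6616.
- s₁² = 0.70 × 0.30 + 0.65 × 0.35 = 0.4375, so s₁ = 0.6614.
- n = (1.960 × 0.6616 + 1.2816 × 0.6614)² / 0.0225 = 204.4, rounded up to 205 per arm. The total is 410 and the power 90.1%.
- The dropout figures also reproduce: 200/0.8 = 250 and 210/0.8 = 262.5, rounded up to 263. Their sum is the stated minimum of 513.

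**2. The error rate if the plan is followed.** At the non-inferiority null boundary, Z₁ and Z₂ are approximately independent standard normal. (Z₁ + Z₂)/√2 then has variance (1 + 1)/2 = 1, and it exceeds 1.96 with probability 0.025. Choosing the stage 2 size from stage 1 data does not alter this, because the weights are fixed. A stop for harm, for futility or because PCC performs worse yields no claim, so it can only lower the chance of a false claim.

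**3. When a claim first becomes possible.** The statistic needs p₁ (200 evaluable patients) and p₂ (at least 210). The earliest confirmatory result is therefore at 410. No hypothesis test is attached to the reviews at 100, 300 or later.

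**4. What it would take to inflate the error.** The documents set no threshold for the reviews, so this is hypothetical. It assumes that a review stops the trial and claims success when z exceeds a chosen value, that the final criterion stays at 1.96, that the barred 200-patient look is excluded, and that review counts are evaluable patients. Simulation of independent normal increments (4,000,000 runs per case, Monte Carlo standard error about 0.0001) gives these one-sided error rates:

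| Statistic at reviews | Total N | Reviews | z > 1.96 | z > 2.576 | z > 3.0 |
|---|---|---|---|---|---|
| Plan's inverse normal | 410 | 300, 400 | 4.0% | 2.6% | 2.5% |
| Plan's inverse normal | 1000 | 300 to 900 | 6.6% | 3.0% | 2.6% |
| Pooled z (not in the plan) | 410 | 100, 300, 400 | 5.7% | 2.9% | 2.6% |
| Pooled z (not in the plan) | 1000 | 100, 300 to 900 | 8.8% | 3.5% | 2.7% |
| No efficacy stop (as planned) | any | – | 2.5% | 2.5% | 2.5% |

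Only the last row describes this trial.

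**5. The sections side by side.** Section 8.6 says what the committee may weigh when it advises. Sections 9.2 and 9.4 and SAP 10.2 say when and how a claim can be made. Section 8.6 supplies no test, threshold or right to declare success, so it does not override them. A committee asked to judge risk against benefit has to look at efficacy, including the possibility that PCC is worse.

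**The case for a change.** The strongest case for a change is that the text does not settle the matter. Futility is named separately, so efficacy need not mean lack of efficacy. The bar is not extended to the 100-patient reviews, the sponsor can terminate in consultation with the IDSMC, and the charter was not available to check. One clause would close the question at almost no cost, and a regulator could fairly ask about repeated unblinded reviews of endpoint data.

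The description of the wording stands: 8.6 and 9.4 are not explicitly tied together, and a clarifying clause would do no harm. What does not follow is that the design has a defect. Harm would require the committee and the sponsor to set aside the end-of-trial test and the stage 2 floor.

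Two supporting arguments are weaker than they look. The 410 targets in 3.3.1.5, 4.1 and 6.2.2, read literally, would also clash with the permitted futility stop, so they do not isolate a conflict about efficacy. And SAP 7.4 describes the interim analysis; it need not repeat a review schedule that the Protocol already gives.

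**Conclusion.** No change is called for. The wording of 8.6 is loose, but the plan as written has one confirmatory test, at the end, with a stage 2 minimum of 210 evaluable patients, and it keeps the one-sided 2.5% level. The sensible reading is that the committee weighs efficacy as part of benefit and risk and makes no early claim of success. A clarifying clause would alter neither alpha, the 1.96 criterion, the sample size nor any planned result.

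This rests on two assumptions: that no review leads to a favourable efficacy stop, which the documents nowhere provide for, and that the charter, not among the documents supplied, does not introduce one. If it did, the size of the problem would depend on its threshold. In the illustrations the error ranges from 2.5% to 2.7% at z > 3.0 and from 4.0% to 8.8% at z > 1.96.

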9 STATISTICAL METHODS AND SAMPLE SIZE

The statistical analysis will be delegated under an agreement of transfer of responsibilities to an external statistician. Details on planned descriptive and exploratory analyses will be provided in a separate Statistical Analysis Plan (SAP).

9.1 Determination of Sample Size

The analysis of the primary efficacy endpoint will involve comparison of haemostatic treatment response to IMP, defined as 'effective' if no additional haemostatic intervention, such as administration of any systemic haemostatic agents (including platelets, cryoprecipitate, fibrinogen concentrate, activated recombinant factor VII, other coagulation factor products or a second dose of IMP) or any haemostatic interventions (including surgical re-opening for bleeding) is required from 60 minutes to 24 hours after initiation of the first dose of IMP.

Patients categorised as having an 'ineffective' haemostatic treatment response to IMP, due to requiring administration of any haemostatic intervention, including a second dose of IMP, in the time window from 60 minutes to 24 hours after initiation of the first IMP dose, will be considered as treatment failures.

Of the more than 100 patients studied in the FARES pilot study, approximately 75% of patients in the PCC group and 65% in the FP group demonstrated haemostatic treatment response from 60 minutes to 24 hours after initiation of the first IMP dose [58]. Using a more conservative estimate of 70% versus 65%, it is estimated that 410 patients will be required to demonstrate non-inferiority with a one-sided α of 0.025, power of $\geq 90\%$ and non-inferiority margin of 0.10 when using a Farrington-Manning score test.

It is anticipated that up to 20% of randomised patients may not meet administration criteria (based on objective Bleeding Severity Scale and INR) due to cessation of haemorrhage between randomisation and delivery of IMP to the operating room and therefore will not receive the therapy.

An administrative unblinded interim analysis will be carried out after 200 evaluable patients have been randomised and treated and will be used to re-estimate the sample size or stop for futility (non-binding) (**Section 9.4**). Patient recruitment will continue during the conduct of the interim analysis. The sample size in the second stage is limited to 210–800 evaluable patients. Accounting for drop-outs as described above, the total sample size will range between 513–1250 if the study is not stopped for futility at the interim (see table below).

	Stage 1	Stage 2 – Minimum	Stage 2 – Maximum	Total - Maximum
Evaluable patients	200	210	800	1000
Sample size including 20% dropouts	250	263	1000	1250

9.2 Statistical Analysis

A formal SAP describing all details of the analyses to be performed will be prepared by the study statistician and approved by the Sponsor prior to study initiation.

The non-inferiority of the primary endpoint 'haemostatic response' will be tested between the treatment groups by means of a Farrington-Manning score test with a non-inferiority margin of 0.10 at a one-sided significance level alpha of 2.5%, testing the null hypothesis as follows:

$$H_0: p(PCC) \leq p(FP) - 0.10$$

will be tested against the alternative

$$H_1: p(PCC) > p(FP) - 0.10$$

where $p(PCC)$ and $p(FP)$ denote the haemostatic response proportions in the PCC and FP treatment groups, respectively.

At the end of the trial, the inverse normal test statistic with equal weights given by

$$(\Phi^{-1}(1 - p_1) + \Phi^{-1}(1 - p_2))/\sqrt{2}$$

is calculated, where p_1 and p_2 denote the p-values for testing the non-inferiority null hypothesis for the first and the second stage of the trial, respectively. If the test statistic exceeds the value 1.96, non-inferiority is demonstrated (see [94]).

Only in case that non-inferiority is demonstrated at the second stage of the study, i.e., the null hypothesis is rejected at the one-sided 2.5% level of significance, superiority of PCC with regard to the primary endpoint will be investigated:

$$H_0: p(PCC) \leq p(FP)$$

will be tested against the alternative

$$H_1: p(PCC) > p(FP)$$

The Farrington-Manning score test will be used to calculate a two-sided 95% confidence interval based on the inverse normal test statistic as given above. This confidence interval corresponds with the test decision for showing non-inferiority and/or superiority [95]. This hierarchical test procedure allows to perform the superiority test at the full alpha of 2.5%.

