9.3 Randomisation, Stratification and Code Release

Eligible patients will be randomly assigned to receive either *Octaplex* or FP. Randomisation lists using a permuted-block, randomisation scheme (stratified by site) will be prepared by the biostatistician. Sealed randomisation envelopes based on the randomisation lists will then be provided to the blood banks/pharmacies of the participating centres who will be responsible for providing the IMP.

Patients will be identified using a sequential numbering system within the centre. Randomisation will then be performed in sequential order of the patient IDs.

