## 10.2. Primary Endpoint

The primary population for the analysis of the efficacy of the IMPs will be the FAS.

The analysis of efficacy will focus on the following primary endpoint:

- P1. Comparison of haemostatic treatment response to *Octaplex* versus FP, defined as 'effective' if no additional haemostatic intervention, such as administration of any systemic haemostatic agents (including platelets, cryoprecipitate, fibrinogen concentrate, activated recombinant factor VII, other coagulation factor products or a second dose of IMP) or any haemostatic interventions (including surgical re-opening for bleeding) is required from 60 minutes to 24 hours after initiation of the first dose of IMP.

The non-inferiority of the primary endpoint 'haemostatic response' will be tested between the treatment groups by means of a one-sided Farrington-Manning score test with non-inferiority margin 0.10 at a significance level of 2.5%, testing the null hypothesis as follows:

$$H_0: p(PCC) \leq p(FP) - 0.10 \text{ will be tested against the alternative } H_1: p(PCC) > p(FP) - 0.10$$

where  $p(PCC)$  and  $p(FP)$  denote the haemostatic response proportions in the PCC and FP treatment groups, respectively.

At the end of the trial, the inverse normal test statistic with equal weights given by

$$(\Phi^{-1}(1 - p_1) + \Phi^{-1}(1 - p_2))/\sqrt{2}$$

is calculated, where  $p_1$  and  $p_2$  denote the p-values for testing the non-inferiority null hypothesis for the first and the second stage of the trial, respectively. If the test statistic exceeds the value 1.96, non-inferiority is demonstrated (see [15]).

Only in case that non-inferiority is demonstrated, i.e., the null hypothesis is rejected at the one-sided 2.5% level of significance, superiority of PCC with regard to the primary endpoint will be investigated:

$H_0: p(\text{PCC}) \leq p(\text{FP})$  will be tested against the alternative  $H_1: p(\text{PCC}) > p(\text{FP})$

The Farrington-Manning score test will be used to calculate a two-sided 95% confidence interval based on the inverse normal test statistic as given above. This confidence interval corresponds with the test decision for showing non-inferiority and/or superiority [16]. This hierarchical test procedure allows to perform the superiority test at the full alpha of 2.5%.

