The analysis of categorical variables (S1, S3, S8, S9, S10, S11, S12) will present relative frequency tables and estimates of the proportions with 95% confidence intervals separately in the treatment groups. The proportions will be compared between the treatment groups in the context of a logistic regression model.

The analysis of continuous variables (S2, S13, S14, S15) will present descriptive statistics of the sampling distribution and the differences between treatment groups. Also, 95% confidence intervals and results of F-test of the treatment group differences will be reported in the context of an ANOVA model.

The analysis of integer count variables (S4, S5, S6, S7) will present descriptive statistics of the sampling distribution and the differences between treatment groups. Treatment group comparisons for variables (S4, S5, S6, S7) will be performed in the context of a counting regression model for the ABCs and their components (SAS PROC GENMOD with Negative-Binomial distribution). Tests and 95% confidence intervals for the treatment group differences will be derived from this statistical model and reported.

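### Randomisation is stratified by centre but the primary test pools centres: mildly conservative if hospitals differ, with a small loss of power

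*Protocol*

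**What the plan says.** Allocation is stratified: "Randomisation lists using a permuted-block, randomisation scheme (stratified by site) will be prepared by the biostatistician" (Protocol 9.3; likewise Protocol 3.3.1.4 and 4.4, and SAP 4.3). Protocol 3.2 expects about 12 hospitals, 10 in Canada and two in the United States.

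The primary test is not stratified. In Protocol 9.2 the response "will be tested between the treatment groups by means of a Farrington-Manning score test with a non-inferiority margin of 0.10"; SAP 10.2 tests it "by means of a one-sided Farrington-Manning score test with non-inferiority margin 0.10 at a significance level of 2.5" per cent. The test is applied in each stage, the two p-values are combined by an inverse normal statistic with equal weights, and "If the test statistic exceeds the value 1.96, non-inferiority is demonstrated".

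For the secondary endpoints, SAP 10.3 names model types without terms. For the binary endpoints, "The proportions will be compared between the treatment groups in the context of a logistic regression model"; continuous endpoints go to an ANOVA and counts to a negative-binomial model. Protocol 9.2.2 speaks only of simple comparisons between the groups. The only planned use of site is a descriptive summary of response by site in SAP 10.4.

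**The concern.** Blocking within centre gives the two arms nearly the same mix of hospitals, so differences between hospitals largely drop out of the treatment difference. The pooled variance still contains them. The standard error is then too large and the test conservative, to the extent that hospitals differ.

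Some difference is plausible. Most events in the primary endpoint are a clinician's decision to give a product or to re-open. Protocol 3.3.1.2 leaves room for judgement within the transfusion protocol, 3.3.1.3 describes hospitals with different characteristics, and 4.6 leaves later haemostatic therapy to institutional practice.

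At stake are a slightly wider confidence interval and some power, more for the superiority step than for non-inferiority. There is also a reproducibility gap: with no model terms listed, whether centre enters the secondary models could be decided after the results are known.

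**Working it through.** **Inputs from the plan.** Response 70% (PCC) and 65% (FP), margin 0.10, one-sided 0.025, power at least 90%, 410 evaluable patients (205 per arm), stages of 200 and 210 (Protocol 3.3.1.5 and 9.1). For superiority, the approximate pilot rates of 75% and 65% (Protocol 9.1).

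**Assumption.** The documents give no between-centre variation. I take the standard deviation (SD) of centre response rates as 0, 5, 10 or 15 points, with the same treatment difference in every centre.

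**Step 1: the plan's own figure.** The restricted estimates under the null are 0.619 and 0.719.
- Null variance sum: 0.6192×0.3808 + 0.7192×0.2808 = 0.4377, so s0 = √(0.4377/205) = 0.0462.
- Alternative variance sum: 0.70×0.30 + 0.65×0.35 = 0.4375, so s1 = √(0.4375/205) = 0.0462.
- Power = Φ[(0.15 − 1.96×s0)/s1] = 90.1%.

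205 per arm is the smallest size that reaches 90%, so 410 reproduces. The equal-weight combination of 200 and 210 without re-estimation also gives 90.1%.

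**Step 2: effect of ignoring centre.** With balance inside centres, the variance of the risk difference falls by 2×SD²/n (n per arm). The pooled test keeps the full variance; the stratified test uses the reduced one.
- Type I error, pooled, at 55% v 65%: 1 − Φ[1.96×√(0.475/(0.475 − 2SD²))], where 0.475 = 0.55×0.45 + 0.65×0.35.
- Non-inferiority power, pooled: Φ[(0.15 − 1.96×√(0.4377/205))/√((0.4375 − 2SD²)/205)]. For the stratified test, subtract 2SD² from 0.4377 as well.
- Superiority power: the same form with 0.10 for 0.15, 0.42 (2×0.70×0.30) for 0.4377, and 0.415 (0.75×0.25 + 0.65×0.35) for 0.4375.

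| Assumed SD (points) | 0 | 5 | 10 | 15 |
|---|---|---|---|---|
| Type I error, pooled (%) | 2.50 | 2.44 | 2.26 | 1.97 |
| Non-inferiority power, pooled (%) | 90.1 | 90.2 | 90.6 | 91.3 |
| Non-inferiority power, stratified (%) | 90.1 | 90.4 | 91.4 | 92.9 |
| N for 90% power, pooled | 410 | 408 | 402 | 392 |
| N for 90% power, stratified | 410 | 406 | 392 | 368 |
| Superiority power, pooled (%) | 59.9 | 60.0 | 60.1 | 60.5 |
| Superiority power, stratified (%) | 59.9 | 60.4 | 62.0 | 64.8 |

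Before rounding, the non-inferiority power forgone is 0.2, 0.8 and 1.6 points (2, 10 and 24 patients). For superiority it is about 0.5, 1.9 and 4.4 points.

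**Step 3: simulation.** Twelve unequal centres, 200 + 210 patients, inverse normal rule; pooled Farrington-Manning against Mantel-Haenszel risk difference with Sato variance. Non-inferiority used 100,000 trials per cell (error about 0.1 point on power). Superiority used 12,000 (error about 0.4 points) and assumed blocks of 4. Entries are pooled / stratified, in %.

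| Assumed SD (points) | 0 | 5 | 10 | 15 |
|---|---|---|---|---|
| Type I error, all treated | 2.57 / 2.52 | 2.51 / 2.54 | 2.35 / 2.54 | 2.07 / 2.48 |
| Non-inferiority power, all treated | 90.4 / 90.3 | 90.6 / 90.7 | 90.6 / 91.2 | 91.1 / 92.4 |
| Non-inferiority power, 20% untreated | 90.2 / 89.8 | 90.3 / 90.0 | 90.6 / 90.9 | 91.2 / 92.3 |
| Superiority power, all treated | 59.9 / 60.0 | 60.5 / 61.6 | 60.8 / 63.3 | 60.5 / 64.8 |
| Superiority power, 20% untreated | 60.5 / 60.6 | 60.5 / 61.2 | 60.3 / 61.9 | 60.7 / 64.3 |

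With 20% untreated and SD 0 or 5, the stratified test is the weaker one for non-inferiority; repeat runs put that loss at about 0.2 to 0.4 points. Sample-size re-estimation was not simulated.

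**The case against.** The strongest reply is that nothing is broken. The plan sizes the trial for the test it uses: "Using a more conservative estimate of 70% versus 65%, it is estimated that 410 patients will be required to demonstrate non-inferiority", with the stated alpha and power "and non-inferiority margin of 0.10 when using a Farrington-Manning score test". That figure reproduces, type I error is not inflated, and the pooled test kept at least 90% power in every scenario. This stands. A reader might infer from the missing stratification that the trial is underpowered or the test invalid; the documents and the arithmetic support neither.

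The size of the loss depends on an unstated quantity. An SD of 15 points would spread centre rates over about 38% to 97% (67.5 ± 1.96×15), and the common transfusion algorithm (Protocol 3.3.1.2 and 4.2.1) makes so wide a spread less likely. The gain in precision is small: the 95% half-width of 9.1 points, 1.96×√(0.4375/205), falls to 8.6 at SD 15, where 0.4375 becomes 0.3925. This stands too, so the loss should be stated as conditional.

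Stratifying has a cost. Each stage has about 17 patients per centre (200/12 to 210/12). Untreated patients, and Canadian patients who refuse consent, leave the analysis set and thin the blocks. The small loss in step 3 reflects this, so a pooling rule is needed.

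A reader might also take SAP 10.3 to leave centre out of the secondary models on purpose. It lists no terms at all, so centre is unspecified; and those endpoints are exploratory. Centre terms could make rare-event models such as S10 and S11 inestimable.

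Lastly, p1 feeds the interim analysis. SAP version 5.0 is dated 28-Oct-2024, and completion was planned for the fourth quarter of 2024. The documents do not say whether the interim has been run. Redefining p1 afterwards would change the prespecified combination test, which is a worse fault than the one being mended.

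**Conclusion.** The point holds as a modest, conditional improvement. The analysis does not reflect the randomisation strata. If hospitals differ by an SD of 5, 10 or 15 points, the pooled test runs at about 2.4%, 2.3% and 2.0% one-sided. It forgoes about 0.2, 0.8 and 1.6 points of non-inferiority power, and about 1, 2 and 4 points of superiority power at 75% versus 65%. The smallest superiority figure is the least certain: 0.5 by formula, 1.1 by simulation. If hospitals do not differ, nothing is lost.

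These sizes rest on the assumed SDs, a constant treatment difference across centres, about 12 centres and no sample-size re-estimation. The omission and the direction of its effect are firm; the magnitude is not. The sample size needs no correction.

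**What to change.** **If the interim has not been run.** In Protocol 9.2 and 9.4 and SAP 7.4 and 10.2, take p1 and p2 from a centre-stratified non-inferiority test within each stage: the Mantel-Haenszel risk difference with Sato variance, or the stratified Miettinen-Nurminen score test. State in advance how small centres, or centres with an empty arm, are pooled, for example within country. Keep the equal weights and the 1.96 boundary, derive the confidence interval from the same test, and keep the pooled test as a sensitivity analysis.

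**If the interim has been run.** Keep the pooled primary test. Add the stratified analysis to SAP 10.4 as a prespecified sensitivity analysis, combined in the same way and with the same pooling rule.

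**Secondary endpoints.** In SAP 10.3, list the model terms and include centre, pooled by the same rule, in the ANOVA, negative-binomial and logistic models. For rare events such as S10 and S11, specify an unadjusted or exact method.

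**Cost.** Wording, a pooling rule and some programming; no new data, since the centre of every patient is known from the stratified lists. The statistical price is the possible 0.2 to 0.4 points of non-inferiority power if centres do not differ and about 20% of patients go untreated.
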